CA055-005 is a bridging study to provide clinical data that will allow extrapolation of the CC-486-AML-001 study data to Japan. This study is designed as a 2:1 randomization of CC-486 or placebo to assess the efficacy and safety of maintenance treatment with oral azacitidine in a cohort

of Japanese participants \geq 55 years with AML and in CR/CRi after conventional induction chemotherapy with or without consolidation chemotherapy. The primary endpoint is RFS because CC-486-AML-001 has successfully shown survival benefit for not only OS but RFS when compared with best supportive care (BSC). The CC-486 dose that has demonstrated tolerability and shown signs of clinical activity in the ORACLE Study is 200 mg. The primary endpoint of RFS and secondary endpoints of OS, time to relapse from CR/CRi, time to discontinuation from treatment, safety, pharmacokinetics (PK), and health-related quality-of-life (HRQoL) will be evaluated and allow for a comprehensive investigation of efficacy, exposure/safety, and HRQoL appropriateness of the clinical recommended dose for the Japanese population in comparison with the data from the Study CC-486-AML-001.

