The QUAZAR Study (CC-486-AML-001) has demonstrated that CC-486 maintenance therapy was associated with significantly longer overall and relapse-free survival than placebo among older patients with AML who were in remission after chemotherapy. CC-486 was approved in the

US and Canada in September 2020 and January 2021, respectively, and is indicated for continued treatment of adult patients with AML who achieved first CR/CRI following intensive induction chemotherapy and are not able to complete intensive curative therapy²⁸. An oral formulation of azacitidine (CC-486) has been developed and is currently being evaluated in clinical trials, either as a single agent or in combination with other drugs, for the treatment of hematological and solid malignancies. This oral formulation of azacitidine provides an opportunity for administration in a more convenient outpatient setting rather than in the hospital/clinic setting. Home administration also alleviates the morbidity of injection and catheter-site reactions and avoids the inconvenience and resource utilization costs associated with frequent hospital/clinic visits.

Results from the ongoing Phase 3, randomized, double-blind, placebo-controlled QUAZAR Study (CC-486-AML-001), which enrolled de novo AML and secondary AML participants, have shown that CC-486 (300 mg/day for 14 days of 28-day treatment cycles) as first-line maintenance therapy demonstrated significant and clinically meaningful improvement in OS and relapse-free survival (RFS) in AML in remission following induction chemotherapy with or without consolidation. Median follow-up was 41.2 months. Median OS was 24.7 months with CC-486 versus 14.8 months with placebo (P=0.0009; HR 0.69 [95% CI 0.55, 0.86]). Median RFS was 10.2 months in the CC-486 arm compared to placebo at 4.8 months (P=0.0001; HR 0.65 [95% CI 0.52, 0.81])²⁹. The RFS rate at the 6-month time point was 67.4% in the CC-486 group and 45.2% in the placebo group, for a difference of 22.2%. The RFS rates were consistently higher for the CC-486 group than for the placebo group at each of the later time points (44.9% versus 27.4% at the 1-year time point and 26.6% versus 17.4% at the 2-year time point, respectively).

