3.3.1 Risk Assessment

Table 3.3.1-1: Risk Assessment

Potential Risk of Clinical Significance	Summary of Data/Rationale for Risk	Mitigation Strategy
Study Intervention(s)		
Known/potential safety risks	
The known side effects associated with azacitidine treatment as very common (a 10% or more chance that this will happen) are:
 
anemia, neutropenia, leukopenia, febrile neutropenia, thrombocytopenia, bronchitis, cellulitis, pneumonia, oral fungal infection, skin infection, respiratory tract infection, upper respiratory tract infection, urinary tract infection, nausea, vomiting, diarrhea,
	
Patients should be monitored closely and appropriate actions taken following recommendations in Section 7.4.1.

Table 3.3.1-1: Risk Assessment

Potential Risk of Clinical Significance	Summary of Data/Rationale for Risk	Mitigation Strategy
	abdominal pain, upper abdominal pain, abdominal discomfort, constipation, asthenia, fatigue, malaise, pyrexia, nasopharyngitis, pharyngitis, laryngeal pain, decreased appetite, weight decreased, hypokalemia, arthralgia, back pain, bone pain, myalgia, musculoskeletal pain, pain in extremity, chest pain, dizziness, headache, insomnia, dyspnea, dyspnea exertional, rash, skin lesion, pruritus, ecchymosis, hematoma, petechiae, and epistaxis.	
Study Procedures		
Study design	Lower dose may not be able to show the comparable results with AML-001 study in spite of consistently observed equivalent exposure of 200 mg in Japanese participants as 300 mg in Caucasian participants.	Although the feasible number of subjects is limited, subjects are enrolled as many as possible. And evaluate comprehensively that the results of not only the primary endpoint but also the secondary endpoints and safety are at least not substantially inconsistent with the results of AML-001 study and also assess in detail the efficacy and safety for individual subjects.
Study design	Small sample size may not be able to show the comparable results with AML-001 study.	Although the feasible number of subjects is limited, subjects are enrolled as many as possible. And evaluate comprehensively that the results of not only the primary endpoint but also the secondary endpoints and safety are at least not substantially inconsistent with the results of AML-001 study and also assess in detail the efficacy and safety for individual subjects.

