10 STATISTICAL CONSIDERATIONS

10.1 Statistical Hypotheses

The primary endpoint is RFS. Based on the median RFS in the CC-486 and placebo groups of Study CC-486-AML-001, the expected median RFS was set at 4.8 months for placebo, and the expected median RFS was set at 9.5 months for CC-486.

As the primary efficacy analysis, a Cox proportional hazards model will be used to estimate the corresponding hazard ratio and 95% CI for CC-486 relative to placebo. RFS curves will be estimated using Kaplan-Meier (KM) methods. The primary objective of this study is to estimate the efficacy of CC-486 as maintenance therapy by using RFS. The study does not plan to conduct any formal statistical hypothetical testing. For participants who do not have an RFS event, their RFS time will be censored at the last contact date (or "last known RFS date"). RFS will be censored at the date of randomization for participants who were randomized but had no response assessment.

Analysis of the primary endpoint will be conducted when the last subject completes 12 months follow-up. However, it may need to be reconsidered depending on the occurrence status of the event.

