10.2 Sample Size Determination

The sample size is primarily calculated as approximately 15 based on the feasibility of enrollment taking into consideration of the anticipated difficulty to find candidates who have achieved CR/CRI with conventional intensive chemotherapy in Japan. However, as many participants as possible will be enrolled.

With a sample size of 15 participants, assuming 2:1 ratio to adequately secure the number of participants in CC-486 group and to keep the number in the placebo group to a minimum, then approximately 10 participants will receive CC-486, and approximately 5 participants will receive

placebo. Based on this sample size, the probability that the point estimate of hazard ratio of CC-486 versus placebo becomes less than 1 is 87%).

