10.4.2 Primary Endpoint(s)

The primary efficacy endpoint of RFS is defined as the time from randomization to the date of documented relapse after CR or CRi per central review, or death from any cause, whichever occurs first. Participants who are still alive without documented relapse after CR or CRi, or who were lost to follow-up without documented relapse, will be censored at the date of their last response assessment. Relapse after CR or CRi is defined according the IWG AML response criteria.

The primary efficacy analysis will be conducted for the ITT Population and will compare the RFS distributions between the two treatment groups. A Cox proportional hazards model will be used to estimate the corresponding hazard ratio and 95% CI for CC-486 relative to placebo. The RFS curves will be estimated for the primary efficacy endpoint, time to the date of documented relapse after CR or CRi or death from any cause, whichever occurs first, using Kaplan-Meier (KM) methods. Kaplan-Meier estimates for median RFS as well as the 25th and 75th percentiles and associated two-sided 95% CIs will be summarized for each treatment group. Plots of the KM survival curves will be presented for the two treatment groups.

Additionally, KM methods will be used to estimate the 1-year and 2-year RFS probabilities for time to death from any cause. Estimates of the 1-year (365 days) and 2-year (730 days) survival probabilities and corresponding 95% confidence intervals will be presented by treatment group.

Additional sensitivity analyses, based on the mITT Population and the ITT Population, will be performed using modified RFS definitions. For these analyses of RFS, participants lost to follow-up without documented relapse will be 1) considered as having an event and 2) considered as having an event if they were randomized to the CC-486 treatment group and censored if they were randomized to the placebo treatment group. The event/censoring time will be the date of the last response assessment.

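### Section 10.4.2 words its 1- and 2-year RFS estimates as time to death, so they would not match the AML-001 RFS rates cited in Section 3.2

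*Combined protocol and SAP*

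**What the plan says.** - **Endpoint.** Section 10.4.2 defines RFS as time from randomization to relapse per central review or death from any cause, whichever is first. It plans a Cox hazard ratio with 95% CI, and Kaplan-Meier (KM) curves, medians and quartiles by arm with 95% CIs.
- **Landmarks.** The same section adds that "KM methods will be used to estimate the 1-year and 2-year RFS probabilities for time to death from any cause". Its next sentence calls the 365- and 730-day values survival probabilities. No 6-month value is planned.
- **Comparator figures.** Section 3.2 gives the AML-001 RFS rates: "The RFS rate at the 6-month time point was 67.4% in the CC-486 group and 45.2% in the placebo group", then "44.9% versus 27.4% at the 1-year time point and 26.6% versus 17.4% at the 2-year time point".
- **Purpose.** Section 3.1 wants to judge efficacy, exposure/safety and the "appropriateness of the clinical recommended dose for the Japanese population in comparison with the data from the Study CC-486-AML-001". Table 3.3.1-1 asks that results be "at least not substantially inconsistent with the results of AML-001 study".
- **Timing.** Section 10.1: "Analysis of the primary endpoint will be conducted when the last subject completes 12 months follow-up". It allows this to be reconsidered depending on events.
- **Sample size.** Section 10.2 bases about 15 participants (10 versus 5) on feasibility and says that the "probability that the point estimate of hazard ratio of CC-486 versus placebo becomes less than 1 is 87" per cent. Section 10.1 plans no hypothesis test.

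**The concern.** RFS is the primary endpoint, and the study exists to be read against AML-001. Landmark RFS rates are the simplest quantities to lay next to the AML-001 rates. The sentence that plans them names RFS but gives the OS event. A programmer who follows the event definition produces OS; one who follows the label produces RFS. In the first case the tables would carry OS rates headed RFS, and the bridging comparison would look better than it is, because survival is never lower than relapse-free survival.

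Two smaller matters sit beside this. The 6-month rate, where the cited AML-001 arms differ most, is not planned. The 2-year rate is planned for an analysis at which there may be no one to estimate it from.

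**Working it through.** **1. The plan's own figure.** Inputs: "the expected median RFS was set at 4.8 months for placebo, and the expected median RFS was set at 9.5 months for CC-486" (Section 10.1), and 10 versus 5 (Section 10.2). With exponential curves HR = 4.8/9.5 = 0.505 and |ln HR| = 0.683. The normal approximation is P(estimated HR < 1) = Φ(√(d × 2/9) × |ln HR|) for d events.
- d = 10: Φ(1.491 × 0.683) = Φ(1.018) = 84.6%
- d = 12: Φ(1.633 × 0.683) = Φ(1.115) = 86.8%
- d = 13: Φ(1.700 × 0.683) = Φ(1.160) = 87.7%

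Simulation with at least 12 months' follow-up gives 85.9% with no accrual spread, 87.5% with 12 months' accrual and 88.2% with 24 months'. The 87% is reproduced.

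**2. The two definitions in Section 10.4.2.** The endpoint is relapse or death. The landmark sentence counts death only, which is the OS event of Section 10.4.3. Both cannot hold for a quantity called RFS.

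**3. Size of a mix-up, from AML-001 figures in Section 3.2.** Median OS was 24.7 and 14.8 months.
- CC-486 at 2 years: 24 < 24.7 months, so OS was at least 50%, against RFS of 26.6%. The gap is at least 50 − 26.6 = 23.4 points.
- Placebo at 1 year: 12 < 14.8 months, so OS was at least 50%, against RFS of 27.4%. The gap is at least 50 − 27.4 = 22.6 points.

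For comparison, the AML-001 treatment differences in RFS are 67.4 − 45.2 = 22.2 points at 6 months, 44.9 − 27.4 = 17.5 at 1 year and 26.6 − 17.4 = 9.2 at 2 years. Reading OS as RFS could thus shift a rate by more than the treatment effect.

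**4. Who is at risk at 2 years.** The documents give no accrual period. I assume uniform accrual over A months and no dropout. A participant entering at month u has A − u + 12 months of potential follow-up at the analysis, so reaching 24 months needs u ≤ A − 12.
- A ≤ 12: nobody.
- A = 24 (the 3-year study duration less 12 months): a fraction 12/24 = 0.5 qualifies. Expected at risk on the AML-001 rates: CC-486 10 × 0.5 × 0.266 = 1.33; placebo 5 × 0.5 × 0.174 = 0.44.
- Chance that nobody is at risk when A = 24: (1 − 0.133)^10 = 24% for CC-486; (1 − 0.087)^5 = 63% for placebo.

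**5. Landmarks against the assessment schedule.** Marrow and response assessments fall on Day 1 of Cycles 3, 6, 9, 12, 15, 18, 21, 24, 30 and 36 (Table 2-2, Section 9.1.1). With 4-week cycles and no delays:

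| Landmark | Assessment before | Assessment after |
|---|---|---|
| 6 months (about week 26) | Cycle 6, week 20 | Cycle 9, week 32 |
| 365 days | Cycle 12, week 44 (day 308) | Cycle 15, week 56 (day 392) |
| 730 days | Cycle 24, week 92 (day 644) | Cycle 30, week 116 (day 812) |

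Section 10.4.2 censors at the last response assessment; Section 10.1 censors at last contact. Under the first rule, an event-free participant with exactly 12 months' follow-up is censored near day 308, before the 1-year landmark. The 6-month landmark does not have this problem, since the week-32 assessment falls within everyone's 12 months.

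**6. What a 6-month rate adds.** Exact binomial, 10 CC-486 participants, at least 6 event-free: 80.2% if the true rate is 67.4%, and 26.6% if it is 45.2%. With complete 6-month data the KM median exceeds 6 months exactly when the KM estimate at 6 months is above 0.5, that is, when at least 6 of 10 are event-free. The planned median therefore carries the same rule.

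**The case against.** The strongest defence is that this is an estimation study whose SAP is still to be written. Section 10.4 says that some analyses may not yield meaningful estimates and that the best available summaries will then be given. Section 10.1 allows the analysis time to move. KM medians and quartiles with CIs are already planned, and the KM plot shows the 6-month value. Most of this stands: the 6-month rate is a convenience rather than a gap, and the 2-year issue depends on an accrual period that the documents do not give. The defence does not reach the landmark sentence, which contradicts the endpoint definition in its own section.

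A reader might go further and infer that Section 10.2 uses a poor operating characteristic and misses a better one. P(estimated HR < 1) is 76–79% on curves through the cited AML-001 rates and about 51% with no effect, while the 6-month rule gives 80% and 27%. The documents do not support that reading, for four reasons.
- The protocol sets no HR < 1 decision rule, and roughly 50% under no effect is what any such point estimate gives, at any sample size.
- The 6-month rule compares one arm with an external rate. As a randomized contrast (higher observed rate, 10 versus 5) it gives 74% versus 43%.
- Its advantage needs AML-001's 45.2% to carry over. If the untreated rate were 55%, the rule would be met 50% of the time with no effect. The rationale for Amendment 02 notes more extensive consolidation.
- It is the same rule as the planned median exceeding 6 months.

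**Conclusion.** The wording of the 1- and 2-year estimates in Section 10.4.2 is wrong and should be corrected. Followed literally, it yields OS rates labelled RFS. By AML-001's own figures these would exceed true RFS by at least 23.4 points for CC-486 at 2 years and at least 22.6 points for placebo at 1 year. That size assumes only that this study resembles AML-001.

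A 2-year RFS estimate has little or no support at the planned primary analysis: nobody at risk with accrual of 12 months or less, and about 1.3 and 0.4 participants with 24 months, assuming uniform accrual and no dropout. A 6-month rate is worth adding because Section 3.2 cites it and all participants have at least 12 months of potential follow-up. It is not a superior operating characteristic that the plan overlooked. The 87% in Section 10.2 is consistent with the Section 10.1 medians and needs no correction. The hazard ratio, sample size and analysis timing are unaffected.

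**What to change.** In Section 10.4.2:
- Delete the reference to time to death from the landmark sentence, or move that sentence to OS in Section 10.4.3. State that landmark RFS is the KM probability of being free of centrally reviewed relapse and alive, by arm, with 95% CIs. Replace the term survival probabilities accordingly.
- Add the 6-month estimate, and present the landmark rates beside the AML-001 rates in Section 3.2.
- State how each landmark relates to the assessments on either side of it (Cycles 6 and 9 for 6 months; Cycles 12 and 15 for 1 year), and reconcile the censoring dates in Sections 10.1 and 10.4.2.
- Report 2-year RFS with numbers at risk, and only at an analysis where follow-up supports it.

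The cost is one corrected sentence, one added landmark and a short rule in the SAP, which is to be finalized before database lock. No new data, visits or participants are needed.

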10.3 Analysis Sets

For the purposes of analysis, the following populations are defined:

Population	Description
Intent-to-treat (ITT)	All participants who have agreed to participate in the study following completion of the informed consent process and registered into the IRT, regardless of whether they received treatment.
Modified intent-to-treat (mITT)	All participants who have met all inclusion/exclusion criteria and experienced no major protocol deviations during the study, and received a minimum of 1 cycle of treatment. Participants who are registered without confirmed CR/CRI per central review will be excluded from the mITT population.
Safety	All participants who received at least 1 dose of study intervention.
Pharmacokinetic (PK)	All participants who received at least 1 dose of study intervention and have measurable plasma concentration data. All analysis of PK data will be based on the PK population.
Health-related Quality of Life	All participants in the ITT Population with a valid health-related quality of life assessment at baseline and at least 1 valid post-baseline assessment.

Abbreviations: CR, complete remission, CRI, complete remission with incomplete blood count recovery; IRT, Interactive Response Technology; ITT, intent-to-treat; mITT, modified intent-to-treat; PK, pharmacokinetic.

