To assess and compare the modified definition of AML relapse being used in this protocol as a criterion for discontinuation from treatment (ie, appearance of > 15% blasts in the bone marrow or peripheral blood) with respect to the IWG definition of relapse after CR or CRi, an exploratory analysis based on the mITT population will be performed for RFS using this modified definition of relapse. For this analysis of RFS, relapse after CR or CRi is defined as the appearance of > 15% blasts in the bone marrow or peripheral blood. Participants who are still alive without documented relapse after CR or CRi or who were lost to follow-up without documented relapse will be censored at the date of their last response assessment.

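### The mITT set is defined by post-randomization facts while RFS is counted from randomization, so the RFS analyses run on it are open to treatment-related selection

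*Combined protocol and SAP*

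**What the plan says.** Section 10.3 (Analysis Sets) builds mITT from four conditions. Two concern status at entry: meeting the eligibility criteria, and remission at registration ("Participants who are registered without confirmed CR/CRI per central review will be excluded from the mITT population"). The other two are that the participant "experienced no major protocol deviations during the study, and received a minimum of 1 cycle of treatment". The section defines neither a major deviation nor what counts as having received a cycle.

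Section 10.4.2 (Primary Endpoint(s)) sets the clock: "The primary efficacy endpoint of RFS is defined as the time from randomization to the date of documented relapse", or death if earlier. It gives no landmark or delayed entry for mITT. The set is used in two places:

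- "Additional sensitivity analyses, based on the mITT Population and the ITT Population, will be performed using modified RFS definitions". These vary the handling of participants lost to follow-up.
- For relapse defined as more than 15% blasts, "an exploratory analysis based on the mITT population will be performed for RFS using this modified definition of relapse". No ITT version is planned.

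The main result rests elsewhere: "The primary efficacy analysis will be conducted for the ITT Population". Section 10.4 leaves further detail on participant selection to an SAP to be finalized before database lock.

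**The concern.** A participant's later course decides whether they belong to the set, but their time is credited from randomization. Two distinct problems follow.

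**Selection.** Treatment can affect both conditions. Section 8.1 lists adverse events, laboratory abnormalities, participant request and protocol violation among the reasons for stopping study drug. Table 3.3.1-1 lists many very common azacitidine toxicities. If such exclusions fall more on one arm, and on participants with a different prognosis, the mITT comparison no longer has the protection of randomization. The deviation condition covers the whole study, so it can remove a participant at any time.

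**Guaranteed event-free time.** If a full cycle must be completed, everyone in the set is event-free for that cycle by construction, and Kaplan-Meier estimates rise.

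At stake is what these analyses can show. Participants lost to follow-up before receiving one cycle are among those the sensitivity analyses mean to count as events, and mITT removes them. The 15% blasts analysis has no ITT counterpart that would reveal a distortion. With about 5 placebo participants, losing one removes a fifth of that arm.

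**Working it through.** **Inputs.** Section 10.1: "the expected median RFS was set at 4.8 months for placebo, and the expected median RFS was set at 9.5 months for CC-486". Sections 5.1 and 10.2: about 10 participants on CC-486 and 5 on placebo. Section 7.1: 28-day cycles with dosing on the first 14 days. Section 10.1: analysis 12 months after the last participant enters. Assumed: exponential RFS, and first dose on the day of randomization. (Table 2-1 allows up to 3 days between them, which would add at most 3/30.44 = 0.10 month to the shifts below.)

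**1. The plan's own figure.** Section 10.2 gives 87% for the probability that the estimated hazard ratio is below 1. The design medians give HR = 4.8/9.5 = 0.505. With d events and 2:1 allocation, P = Φ(√(d × 2/9) × |ln 0.505|). For d = 12 this is Φ(1.633 × 0.683) = 86.8%. Accrual length is not stated. Accrual of 0 to 24 months gives 10.0 to 12.8 expected events and 84.5% to 87.5%. The figure is reproduced, so the exponential model at these medians is a fair basis for the rest.

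**2. Early events.** P(event by t) = 1 − exp(−ln 2 × t/median), with 28 days = 0.92 month and 14 days = 0.46 month.

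| Meaning of one cycle | Placebo | CC-486 | At least 1 of 15 has an event in that time |
|---|---|---|---|
| 28 days completed | 12.4% | 6.5% | 1 − 0.876⁵ × 0.935¹⁰ = 74% |
| 14 dosing days | 6.4% | 3.3% | 49% |
| Cycle 1 started | about 0 | about 0 | about 0 |

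For 28 days the expected numbers are 5 × 0.124 = 0.62 and 10 × 0.065 = 0.65, about 1.3 of 15.

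**3. Effect on Kaplan-Meier estimates.** Among those event-free to time c, S(t)/S(c) = 0.5 at t = c + median.

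| 28-day reading | Placebo, ITT → mITT | CC-486, ITT → mITT |
|---|---|---|
| Median (months) | 4.8 → 5.7 | 9.5 → 10.4 |
| 1-year RFS | 17.7% → 17.7/0.876 = 20.2% | 41.7% → 41.7/0.935 = 44.6% |

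The 14-day reading adds 0.46 month to each median.

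These are upper values for this mechanism, because they treat every early RFS event as an exclusion from mITT. The protocol does not work that way. Participants with 5% to 15% blasts may stay on treatment (Sections 5.1 and 7.4.2), and stopping for relapse requires more than 15% (Section 8.1). The first scheduled on-treatment marrow is at Cycle 3 (Table 2-2).

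**4. Effect on the hazard ratio of guaranteed time alone.** The Cox likelihood compares participants still at risk at each event time. Removing everyone with an event before c deletes the early terms and leaves the later risk sets intact. Under proportional hazards the ratio stays at 0.505 in both sets, or at 1.00 in both under no effect.

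**5. Effect of selection that differs by arm.** The documents give no rates, so this is illustrative only. Assume 20% to 30% of each arm is frail with 2 to 3 times the hazard, and 25% to 100% of frail CC-486 participants leave mITT in Cycle 1, on top of the 28-day condition.

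| Within-stratum HR | ITT HR | mITT HR |
|---|---|---|
| 1.0 | about 1.0 | 0.98 to 0.83 |
| 0.505 | 0.52 to 0.55 | 0.53 to 0.43 |

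In every scenario the mITT ratio was below its own ITT counterpart. That direction follows from the assumption that frail CC-486 participants are the ones who leave.

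**The case against.** The strongest reply is that little depends on mITT. The primary analysis is ITT, there is no hypothesis test, and the loss-to-follow-up analyses are run on both sets, so a divergence would be visible. The mITT-only analysis is labelled exploratory. With about 12 events the standard error of the log hazard ratio is 1/√(12 × 2/9) = 0.61, a 95% interval of roughly a factor of 3.3 each way, so a shift of up to 0.9 month is small beside the noise. All of this stands, and it is why the point is a cheap improvement and not a threat to the trial's main result.

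Three stronger readings are tempting, and the documents do not support them:

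- A reader might infer that anyone who relapses or has toxicity in Cycle 1 is dropped. Low-level blasts do not end treatment, and Section 7.4.1 mostly directs interruption, resumption or reduction for toxicity.
- A reader might infer that the guaranteed time biases the hazard ratio. Under proportional hazards it does not (step 4).
- A reader might infer that inflated mITT medians will be set against those of CC-486-AML-001. No section says so. Kaplan-Meier medians are specified with the primary ITT analysis, and Table 3.3.1-1 describes a broad comparison without mentioning mITT.

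Two further replies do not succeed. Deferral to the SAP can settle what a major deviation or one cycle means, but Section 10.3 already makes both of them conditions of membership. It is also true that requiring one dose is itself a post-randomization condition. However, randomization is within 3 days of Cycle 1 Day 1 and treatment is blinded, so assignment has little room to influence whether the first dose is taken.

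**Conclusion.** The concern holds in a limited form. As written, mITT conditions on the post-randomization course while RFS starts at randomization. The mITT sensitivity analyses are therefore open to treatment-related selection, and the 15% blasts analysis most of all because it has no ITT version.

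The guaranteed event-free time inflates Kaplan-Meier medians at the design values by at most about 0.9 month per arm if a cycle means 28 completed days. The inflation is about half that for 14 dosing days and almost nothing if Cycle 1 need only be started. These figures assume exponential RFS and treat every early event as an exclusion.

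Any hazard-ratio bias depends on exclusions that differ by arm. The documents do not allow its size or direction to be fixed, and the ranges in step 5 only illustrate it. The whole-study deviation condition remains a source of selection whichever meaning of a cycle is adopted. The primary ITT estimate is not touched.

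**What to change.** In Section 10.3 and the SAP, define mITT by facts settled at or before first dose: randomized, eligibility met, screening CR/CRi confirmed by central review, and at least one blinded dose taken. Move the deviation and one-cycle conditions to a separate set labelled per-protocol, define both terms there, and do not use that set for the RFS sensitivity analyses. In Section 10.4.2, run the 15% blasts analysis on ITT as well.

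The cost is one revised definition and one additional run of an analysis already planned. No new data are needed. The downside is that mITT becomes a less pure on-treatment set.
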